7.1.1.2 Laboratory values and ECG findings

Changes in laboratory values or ECG parameters are only considered to be AEs if they are judged to be clinically significant (i.e., if some action or intervention is required or if the Investigator judges the change to be beyond the range of normal physiologic fluctuation). A laboratory re-test and/or continued monitoring of an abnormal value are not considered an intervention. In addition, repeated or additional non-invasive testing for verification, evaluation or monitoring of an abnormality is not considered an intervention.

If abnormal laboratory values or ECG findings are the result of pathology for which there is an overall diagnosis (e.g., increased creatinine in renal failure), the diagnosis only should be reported appropriately as an AE.

7.1.1.3 Pre-existing conditions

For STRIDE subjects the handling of pre-existing conditions (present at the time of signing of informed consent) will be dependent on their reporting in the STRIDE study and when the subject is enrolled into this study.

If the subject is enrolled at the STRIDE Week 24 or FU visits the following will apply:

- If the condition was reported as an ongoing AE at the end of the STRIDE study then the details concerning the AE will be transferred to a PTE eCRF page in this study and followed up during this study.
- If the condition was reported as pre-existing in the STRIDE study (i.e., present at the time of signing STRIDE informed consent) then it would have been reported in medical history for STRIDE. Such information will be transferred to this study's database and may be updated (e.g., end date provided).

For mtDNA-PMM subjects enrolled from Study REN001-101 or after exiting STRIDE, and nDNA-PMM subjects, then the following will apply:

- Baseline evaluations (e.g., laboratory tests, ECG, X-rays etc.) should NOT be recorded as PTEs.
- Pre-existing conditions (present at the time of signing REN001-202 informed consent) are considered concurrent medical conditions and should be recorded as medical history. They should NOT be recorded as PTEs. However, if the subject experiences a worsening or complication of such a concurrent condition, the worsening or complication should be recorded appropriately as a PTE/AE. Investigators should ensure that the event term recorded captures the change in the condition (e.g., "worsening of..."). For example,
 - episodic conditions asthma or epilepsy: if episodes become more frequent, serious or severe in nature, the AE term recorded should capture the change in the condition from baseline (e.g., "worsening of...").
 - degenerative concurrent conditions (e.g., cataracts): if the worsening of the condition occurs to a greater extent to that which would be expected the AE term recorded should captures the change in the condition from baseline (e.g., "worsening of...").

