3.2 Endpoints

3.2.1 Primary Endpoints

For mtDNA and nDNA subjects:

- Number and severity of adverse events (AEs)
- Number of AEs leading to study drug discontinuation
- Number of serious adverse events (SAEs)
- Number of adverse events of special interest (AESI)
- Number of AEs leading to death

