7.1.1.5 Adverse Events of Special Interest (AESI)

AESI are those of scientific and medical concern specific to the Sponsor's product for which ongoing monitoring and rapid communication by the Investigator to the Sponsor may be warranted. These events require further investigation to fully characterize. Based on this assessment, the Sponsor plans to include AESI as follows:

- Changes in laboratory parameters of muscle injury associated with clinically significant AEs
- Changes observed after baseline in formation or exacerbation of cataracts.
- Occurrence of fractures after baseline

While an AESI may not meet the definition of an SAE, it should be reported in the same manner as SAE (See [Section 7.1.1.9](#)). This allows the event to be tracked in more detail and followed up for additional information if required. When completing the SAE form there is an extra box to check to confirm that the event is an AESI. AESIs will not be reported to the Regulatory Authorities unless they are also suspected unexpected serious adverse reactions (SUSARs).

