6.1. ADVERSE EVENTS

The incidence, causality and severity of treatment-emergent adverse events (TEAEs), including treatment-emergent serious adverse events (TESAEs) and adverse events of special interest (AESI), will be investigated.

AESI are those of scientific and medical concern specific to mavodelpar and include:

- Changes in laboratory parameters of muscle injury associated with clinically significant adverse events (AEs)
- Changes observed after baseline in formation or exacerbation of cataracts.
- Occurrence of fractures after baseline

AESI will be identified on the eCRF and will be reported in the same way as serious adverse events (SAEs).

Note in Protocol Versions 1.0 and 2.0, a spherical equivalent loss of ≥ 0.75 diopters (regardless of changes in lens clarity) was also considered an AESI and reported on the eCRF. However, since the implementation of Protocol Version 3.0 these are no longer routinely reported as AESIs.

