6.7. EYE EXAMINATIONS

Eye examination data will be performed during the study by an appropriately qualified professional. Any abnormality considered clinically significant, will be reported as an AE.

To allow for scheduling of the eye examinations the REN001-201 Week 24 (Month 6) assessment can occur up to 14 days after the visit. Hence, this examination could occur after the start of administration of mavodelpar in REN001-202; this period is not considered sufficient time to have an impact on eye examination results. Therefore, for those mtDNA-PMM subjects who received placebo in REN001-201, enrolled in REN001-202 at REN001-201 Exit, enrol from study REN001-101 or for nDNA-PMM subjects this record will still be considered the baseline record relative to the start of mavodelpar provided it occurs within 14 days of the first dose of mavodelpar.

Baseline eye examinations will not be required for REN001-201 Exit subjects if the screening visit is within 6 months of the last REN001-201 examination.

Best corrected visual acuity (BCVA) can be assessed using the LogMAR scale, ETDRS letters or Snellen line. All results will be converted to the LogMAR scale before calculating changes from baseline at each visit for left and right eye BCVA (Roy 2003).

Where the Snellen scale has data recorded as x/y the MAR value is calculated by dividing y by x and then the LogMAR is the base 10 logarithm of the MAR value [i.e., $\text{LogMAR} = \log_{10}(\text{MAR})$]. Hence, higher scores indicate worse BCVA and increases from baseline indicate deterioration.

A change of 0.02 in LogMAR is equivalent to 1 letter. Hence, a Snellen scores with ‘-z’ or ‘+z’ indicating z letters fewer, or z letters more, respectively, will require an adjustment to the LogMAR score; 0.02 will be added or subtracted, respectively, for each letter (z).

e.g.,

$$20/15-1: \text{LogMAR} = \text{Log}_{10}(15 \text{ divided by } 20) + 0.02 = -0.105$$

$$20/15+1: \text{LogMAR} = \text{Log}_{10}(15 \text{ divided by } 20) - 0.02 = -0.145$$

If the Snellen scale is not reported in x/y format or x/y±z format, then the conversion to logMAR will not be done.

A change of 0.3 LogMAR (equivalent to 15 letters or 3-line change) is considered meaningful.

Refraction error based on spherical equivalent will be derived for each eye using the following formula:

$$\text{Spherical Equivalent (diopters)} = \text{cylinder (diopters)}/2 + \text{sphere (diopters)}$$

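### For a cataract already present at consent, Protocol 7.1.1.3 and 7.1.1.5 give different recording rules, so cataract exacerbations in the AESI count (a primary endpoint) may be ascertained inconsistently between sites and entry routes

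*Protocol*

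**What the plan says.** Protocol 7.1.1.3 handles pre-existing conditions by entry route.

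- **Options 3 and 4.** The list opens "For mtDNA-PMM subjects enrolled from Study REN001-101 or after exiting STRIDE, and nDNA-PMM subjects, then the following will apply". Its general rule is that "if the subject experiences a worsening or complication of such a concurrent condition, the worsening or complication should be recorded appropriately as a PTE/AE". Examples of how to word the event term follow, and one concerns "degenerative concurrent conditions (e.g., cataracts): if the worsening of the condition occurs to a greater extent to that which would be expected"; in that case the term should capture the change from baseline.
- **Options 1 and 2** (rollover at STRIDE Week 24 or follow-up). A condition that was an ongoing AE in STRIDE is carried over as a pre-treatment event. A condition that predated STRIDE sits in medical history: "Such information will be transferred to this study's database and may be updated (e.g., end date provided".

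Protocol 7.1.1.5 lists as an AESI, for all subjects, "Changes observed after baseline in formation or exacerbation of cataracts". It is to be reported in the manner of an SAE. SAP 6.1 repeats that definition and adds "AESI will be identified on the eCRF and will be reported in the same way as serious adverse events (SAEs". The number of AESIs is a primary endpoint (Protocol 3.2.1). On eye examinations SAP 6.7 says "Any abnormality considered clinically significant, will be reported as an AE".

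**The concern.** Cataract is a named risk (Protocol 1.4.2.2) and the reason eye examinations are included in the REN001 trials. For a subject with an existing lens opacity, the example in 7.1.1.3 invites the investigator to ask whether the progression is more than expected before recording it. Neither document says what is expected, in LOCS III grades or otherwise, and this study has no concurrent control arm from which to judge it. Section 7.1.1.5 asks no such question.

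Two sites seeing the same change in grade could therefore act differently and each point to the protocol. Because the AESI count is taken from what the site flags, the difference passes straight into a primary endpoint. It also enters the comparison of nDNA with mtDNA subjects, which SAP section 2 names as bridging data for safety. The recording text differs by entry route, and entry route is tied to mutation group: every nDNA subject enters by Option 4, and most mtDNA subjects are expected to enter by Option 1.

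**Working it through.** The plan states no figure on this point, so the check is mainly a comparison of texts. Take a subject whose cataract was present before consent and whose LOCS III grade rises after baseline by an amount the examiner regards as ordinary.

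| Text | Who it covers | Is the change recorded? |
|---|---|---|
| Protocol 7.1.1.3, general sentence | Options 3 and 4 | Yes; any worsening |
| Protocol 7.1.1.3, cataract example | Options 3 and 4 | Can be read as no; the extent is not beyond expectation |
| Protocol 7.1.1.3, medical-history bullet | Options 1 and 2 | Not stated; the history may be updated |
| Protocol 7.1.1.4 | All, but only for a pre-treatment event or AE | Yes, as a new AE, if the cataract was carried over as an ongoing STRIDE AE; silent if it is medical history |
| Protocol 7.1.1.5 and SAP 6.1 | All | Yes, as an AESI |
| SAP 6.7 | All | Yes if clinically significant; silent otherwise |

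Three things follow.

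1. Within Options 3 and 4 the cataract example sits against both the sentence it illustrates and the AESI definition. It also fits poorly with Protocol 7.1.1.1, where an AE needs no causal link and worsening in severity after the first dose makes it treatment-emergent.
2. For Options 1 and 2 there is no threshold, but for medical-history conditions there is no explicit instruction in 7.1.1.3 either. Only 7.1.1.5 applies.
3. The SAP derives no AESI from LOCS III grades. An exacerbation that is not recorded and flagged is not counted.

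**Share of subjects under the 7.1.1.3 example.** Inputs: about 150 mtDNA and up to 50 nDNA subjects (Protocol 4.5 and 8.2.2). The number of Option 3 subjects is not given; I assume 0 to 30 of the 150.

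- Lower: (50 + 0) / 200 = 25%
- Upper: (50 + 30) / 200 = 80 / 200 = 40%

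The other 60% to 75% (120 to 150 of 200) are rollovers covered by the Option 1 and 2 text. These shares count everyone on the route. The subjects affected are those with a cataract at consent that later progresses, and the documents give no figure for either proportion.

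**The case against.** The best defence is that the protocol nowhere says worsening is recorded only if it exceeds expectation. The governing sentence asks for any worsening, the cataract line is one of two examples about wording the event term, and the dedicated AESI section is unconditional for every route. A careful site would report the event. That stands as far as it goes: the text contradicts itself and does not plainly order omission. It does not remove the problem, because the example attaches a condition to cataracts by name and nothing says which passage prevails.

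Four stronger readings are tempting, and the documents do not support them.

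- *Slow progression drops out of the study.* It does not. LOCS III change is summarised by visit and for the worse eye (SAP 12.7), eye assessments are a secondary endpoint for both mutation groups (Protocol 3.2.2), and the Safety Review Committee reviews eye examinations directly (Protocol 3.11). What is at risk is the AE and AESI count and the reporting that goes with it. The graded summaries are not a full substitute: the SAP sets no LOCS III criterion, although Protocol 3.2.2 lists the incidence of potentially clinically significant eye changes as an endpoint.
- *New cataracts are missed.* The example concerns only conditions present at consent.
- *nDNA counts are biased low against rollovers.* Options 3 and 4 have an explicit instruction to record worsening, and Options 1 and 2 have none for medical-history conditions. Under-recording could fall on either side. The mtDNA group also contains Option 3 subjects under the same text as nDNA subjects.
- *SAP 6.7 is a further filter.* It says that clinically significant findings are reported; it does not say that others are not.

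**Conclusion.** The plan is wrong as written on a narrow point. For subjects entering by Option 3 or 4 with a cataract at consent, 7.1.1.3 contains an undefined condition that conflicts with its own general sentence and with 7.1.1.5 and SAP 6.1. For Options 1 and 2 the same section leaves worsening of a medical-history condition unaddressed. The consequence is possible inconsistent ascertainment of cataract exacerbation in a primary safety count and in the bridging comparison, in a direction that cannot be determined from the documents.

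The 7.1.1.3 example reaches 25% to 40% of planned subjects, if both groups fill and Option 3 contributes 0 to 30. The number actually affected is smaller and cannot be calculated. The study is descriptive, with no formal testing, so no inference is invalidated. The conclusion rests on some sites reading the example as a threshold, which its wording permits but does not compel.

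**What to change.** Reconcile the passages so that one rule applies to all entry routes:

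- Remove cataracts from the degenerative-condition example in Protocol 7.1.1.3.
- Add a sentence such as: for all enrolment options, any post-baseline formation or exacerbation of cataract is recorded as an AE and as an AESI under 7.1.1.5, whatever progression was expected; expectedness is considered in the causality assessment.
- Cross-refer SAP 6.7 to that rule.

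This is a small edit in each document. It brings somewhat more AESI reports, some of them age-related. It does not define how large a LOCS III change counts as exacerbation, so examiner judgement remains. A cross-check of AESI flags against a pre-specified LOCS III change would show where flags and grades disagree, including at visits recorded under the present text.

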7.1.1.4 Worsening of PTEs and AEs

If the subject experiences a worsening or complication of PTE or an AE after starting the study drug in this study, the worsening or complication should be recorded as a new AE. Investigators should ensure that the AE term recorded captures the change in the condition (e.g., "worsening of...").

7.1.1.5 Adverse Events of Special Interest (AESI)

AESI are those of scientific and medical concern specific to the Sponsor's product for which ongoing monitoring and rapid communication by the Investigator to the Sponsor may be warranted. These events require further investigation to fully characterize. Based on this assessment, the Sponsor plans to include AESI as follows:

- Changes in laboratory parameters of muscle injury associated with clinically significant AEs
- Changes observed after baseline in formation or exacerbation of cataracts.
- Occurrence of fractures after baseline

While an AESI may not meet the definition of an SAE, it should be reported in the same manner as SAE (See [Section 7.1.1.9](#)). This allows the event to be tracked in more detail and followed up for additional information if required. When completing the SAE form there is an extra box to check to confirm that the event is an AESI. AESIs will not be reported to the Regulatory Authorities unless they are also suspected unexpected serious adverse reactions (SUSARs).

7.1.1.6 Assessment of Adverse Event

Each AE will be assessed by the Investigator with regard to the following categories.

7.1.1.6.1 Seriousness

An SAE (or serious ADR or unexpected SAE) is defined as any untoward medical occurrence that at any dose:

- Results in death.
- Is life-threatening (this means that the subject is at risk of death at the time of the event; it does not mean that the event hypothetically might have caused death if it were more severe).
- Requires inpatient hospitalisation or prolongs existing hospitalisation.
- Results in persistent or significant disability or incapacity.
- Is a congenital anomaly or birth defect.
- Is an important medical event(s) that may not be immediately life-threatening or result in death or hospitalisation but that may jeopardize the subject or require intervention to prevent one of the above outcomes. Examples of such medical events include allergic bronchospasm requiring intensive treatment in an emergency room or at home, blood dyscrasias or convulsions that do not result in subject hospitalisation, or the development of drug dependency or drug abuse.

Note: Cases of potential drug-induced liver injury as assessed by laboratory test values (“Hy’s Law Cases”) are also reportable. If a subject develops abnormal values in AST or ALT or both, concurrent with abnormal elevations in total bilirubin and no other known cause of liver injury, that event would be classified as a Hy’s Law Case. In this clinical study, the term SAE will be understood to also include Hy’s Law Cases.

Medical and scientific judgment should be exercised in deciding whether a case is serious and whether expedited reporting is appropriate.

7.1.1.6.2 Severity

The intensity of each AE must be assessed by the Investigator using one of the following categories, and recorded in the eCRF:

- Mild: An AE that does not interfere with usual activities.
- Moderate: An AE that interferes with usual activities.
- Severe: An AE that prevents usual activities.

7.1.1.6.3 Causality

The Investigator will assess the causality / relationship between the study drug and the AE and record that assessment in the eCRF. Causality will be shown as Related, Possibly Related, or Not related.

7.1.1.7 Relationship to Study Procedures

Relationship (causality) to study procedures should be determined for all AEs.

The relationship should be assessed as Yes if the Investigator considers that there is reasonable possibility that an event is due to a study procedure. Otherwise, the relationship should be assessed as No.

7.1.1.8 Collection and Reporting of AEs

7.1.1.8.1 PTE and AE Collection Periods

Collection of PTEs will commence from the time the subject signs the informed consent to participate in the study and continue until the subject is first administered study drug (Day 1) or until screen failure.

Collection of AEs will commence from the time that the subject is first administered study drug (Day 1). Routine collection of AEs will continue until the follow-up telephone contact (if required, see [Section 6.14](#)) approximately 30 days after the last study drug dose.

7.1.1.8.2 PTE and AE Reporting

AEs at the end of the STRIDE study for subjects enrolled at the STRIDE Week 24 or FU visits that are still present at the time the subject signs the informed consent to participate in this study should be followed up in this study and recorded in the eCRF as PTEs.

At each study visit, the Investigator will assess whether any subjective AEs have occurred. A neutral question, such as “How have you been feeling since your last visit?” may be asked.

Subjects may report AEs occurring at any other time during the study.

All subjects experiencing AEs, whether considered associated with the use of the study drug or not, must be monitored until the symptoms subside and any clinically relevant changes in laboratory values have returned to baseline or until there is a satisfactory explanation for the changes observed. All PTEs/AEs will be documented in the PTE/AE page of the eCRF, whether or not the Investigator concludes that the event is related to the study drug. The following information will be documented for each event:

- Event term
- Start and stop date {and time}
- Severity
- Investigator’s opinion of the causal relationship between the event and administration of study drug
 - If no, provide alternative aetiology or explanation
- Investigator’s opinion of the causal relationship to study procedure(s), including the details of the suspected procedure
- Action concerning study drug
- Outcome of event
- Seriousness.

7.1.1.9 Reporting Serious Adverse Events

All SAEs that occur during the study from the signing of the informed consent and up to approximately 30 days after receiving the last dose of study drug, whether considered to be associated with the study drug or not, must be reported within 24 hours by email or fax to the study Pharmacovigilance (PV) team. The minimum information required for an initial report is:

- Sender of report (name, address of Investigator)

- Subject identification (screening number, initials, NOT subject name)
- Protocol number
- Description of SAE and reason why the event is categorized as serious
- Causality assessment, if possible

As far as possible all points on the SAE form should be covered in the initial report and the completed SAE form faxed to the PV team (details below). The original SAE form should be sent to the address below and the Medical Monitor and the Sponsor Chief Medical Officer informed by email. In addition, the event must be documented in the eCRF.

SAE information to be sent to PV Team:

**Bionical Emas
[name]
[name]**

**[name]
[name]**

United Kingdom

Email: [contact]

[contact]

After receipt of the initial report, the PV team will review the information and, if necessary, contact the Investigator, to obtain further information for assessment of the event. Bionical Emas, the PV vendor will be responsible for all information processing and reporting according to local legal requirements. Where necessary, Investigators will inform the authorities in their own countries.

7.1.1.10 Reporting Pregnancies

Although pregnancy should not be considered as an SAE *per se*, any pregnancies occurring in a study subject between baseline and the end of the contraception requirements (14 weeks after last dose for males, 30 days (approximately 1 menstrual cycle) after last dose for WOCBP) must be reported and captured as if they were SAEs.

If any subject is found to be pregnant during the study, the subject should be withdrawn, and study drug should be immediately discontinued. In addition, any pregnancies in the partner of a male subject during the study or for 14 weeks after the last dose of study drug should also be recorded following authorisation from the subject's partner.

All reported pregnancies will be followed up to final outcome, using the paper pregnancy follow-up form. The outcome, including any premature termination, must be reported to the Sponsor. An evaluation after the birth of the child will also be conducted.

Reports should be sent within 24 hours using the Pregnancy Report Form. If the female subject and/or female partner of a male subject agrees to the primary care physician being informed, the Investigator should notify the primary care physician that the subject/female partner of the subject was participating in a clinical study at the time she became pregnant and provide details of treatments the subject received.

